1.3 Number of Patients

The sample size was derived under the assumptions that the number of VOCs has a negative binomial distribution with shape parameter 0.8 and that the mean number of crises per year is 2.0 in the placebo group with reduction of 50% in the ticagrelor group. Considering that patients will be randomised in a 1:1 ratio, with minimum follow-up of 12 months and average follow-up of 18 months, 154 patients will provide about 90% power for a 2-sided test of the mean number of crises for ticagrelor versus placebo, at significance level 5%. Allowing for dropouts, the sample size is increased to 182. The calculations were based on simulation with 5,000 repetitions. Scenarios and simulations were evaluated to assess the risk with shorter and longer mean follow-up time. To ensure that the study is adequately powered the recruitment rate will be monitored and the sample size may be adjusted to a maximum of 200 patients. With a mean follow-up time of 13 months, 200 patients will provide 90% power to detect a reduction of 50% in the ticagrelor group.

The randomisation codes will be computer-generated by Parexel Informatics and loaded into the Interactive Voice/Web Response System (IxRS) database. Randomisation codes will be generated in blocks to ensure approximate balance (1:1) between the two randomised treatment groups (ticagrelor or placebo twice daily [bd]). Stratification for baseline hydroxyurea use (Yes/No) by country will be applied.

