The significance level for the primary endpoint will be 2-sided 5%; confidence intervals will be 95%. 2-sided p-value < 0.05 will be considered statistically significant.

No multiplicity adjustment will be included as no formal testing on secondary endpoints for statistical significance will be carried out. Statistical testing of secondary efficacy endpoints is only for exploratory purposes.

In general, and unless otherwise specified, ticagrelor data will be pooled and analysed irrespective of weight-based dose (15 mg/30 mg/45 mg bd). Therefore, all summaries will be presented by treatment group as follows:

Ticagrelor 15/30/45 mg bd	Placebo	Total
--------------------------------------	----------------	--------------

Study treatment exposure and compliance, as well as PK and PD data will be analysed according to pooled dose as well as separately per weight-band of dose, overall and/or at the time of assessment, as relevant. Summaries may, therefore, be presented by treatment group as follows, where relevant:

Ticagrelor 15/30/45 mg bd	Ticagrelor 15 mg bd	Ticagrelor 30 mg bd	Ticagrelor 45 mg bd
--------------------------------------	--------------------------------	--------------------------------	--------------------------------

Individual data (scheduled and unscheduled) will be presented in patient data listings. Safety data, PK, and PD listings will be sorted by actual study treatment and E-code number. All other patient data listings will be sorted by patient identifier and planned treatment group.

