^bAll patients withdrawing for a COVID-19 related reason, regardless of which category of reason is collected for them, will be reviewed prior to study unblinding

In addition, a tipping point analysis will be performed (if appropriate, ie, the primary efficacy was a favourable result) using the same model as above and where:

- Missing counts for a patient will be imputed, according to the rate of the double-blind randomised treatment group that the patient belongs to multiplied by a factor delta (δ).
- A series of analyses will be performed with a range of increasing deltas for the two treatment groups (δ_P and δ_T for placebo and ticagrelor groups respectively) so that one can assess at which point the study conclusions would change from favourable to unfavourable; ie, to identify a tipping point.

In this assessment, the ticagrelor group is assumed to worsen after withdrawal. Therefore, deltas will be increased starting from 1 in increments of 0.025, until a favourable primary efficacy result is no longer favourable. If statistical significance is maintained among the matrix of possible δ combinations, the comparison is deemed robust to missing data.

Together with the primary analysis the sensitivity analyses are considered to cover the range from realistic to plausible worst-case assumptions about missing data. The MAR multiple imputation approach is expected to correspond closely to the primary analysis and is included to allow for comparisons with MNAR assumptions using the same multiple imputation methodology.

The pDRMI/DRMI approach was selected as the most conservative approach because placebo patients are potentially receiving standard of care and are not expected to change to a substantially more effective treatment after withdrawing from study or double-blind randomised study treatment. For patients receiving ticagrelor who withdraw from the study due to study treatment-related reasons it is assumed that at worst they would be on the standard of care treatment ie, the placebo group.

On-treatment Analyses (Efficacy and Effectiveness estimands)

In addition, primary and sensitivity analyses described previously, two alternative estimands will be estimated using only the initial randomised study treatment data:

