Default definition for $p_{j,1}$ and $p_{j,2}$ based on formula (2). ***		$p_{j,2} = p_{j,1}$ For all treatment groups j=T and P	$p_{j,2} = p_{j,1}$ For all treatment groups j=T and P with δ multiplied by imputed values. incrementing δ by 0.025 at each iteration	$p_{B,2} = p_{B,1}$ $p_{B,2} = p_{P,1}$ $p_{P,2} = p_{P,1}$ for reasons above otherwise $p_{B,2} = p_{B,1}$	$p_{B,2} = p_{B,1}$ $p_{B,2} = p_{P,1}$ $p_{P,2} = p_{P,1}$ for reasons above otherwise $p_{B,2} = p_{B,1}$		$p_{j,2} = p_{j,1}$ For all treatment groups j=T and P	$p_{B,2} = p_{B,1}$ $p_{B,2} = p_{B,1}$ $p_{B,2} = p_{P,1}$ $p_{P,2} = p_{P,1}$ for reasons above otherwise $p_{B,2} = p_{B,1}$	$p_{B,2} = p_{P,1}$ $p_{P,2} = p_{P,1}$ for reasons above otherwise $p_{B,2} = p_{B,1}$
---	--	---	--	--	--	--	---	---	---

P Placebo. T Ticagrelor.

* Implicitly assumes unobserved rate is the same as observed.

** All patients withdrawing from placebo have VOC event rate imputed using the placebo treatment group rate. (i.e. $p_{P,2} = p_{P,1}$).

*** Note can be over written by review prior to database lock and routine study unblinding.

Forest plots will be used to show the primary analysis results along with the missing data sensitivity and alternative estimand analysis results.

It is noted that if the primary analysis is statistically significant, it is not necessarily expected that all sensitivity analyses will also give statistically significant results. If the results of the sensitivity analyses provide reasonably similar estimates of the treatment effect to the primary analysis, this will be interpreted as providing assurance that neither the lost information nor the mechanisms which cause the data to be missing have an important effect on primary analysis conclusions. Based on these outputs and the study treatment's mechanism of action, the plausibility of the assumptions made about missing data in the different analyses will be considered and described in the CSR.

SIGNATURE PAGE

This is a representation of an electronic record that was signed electronically and this page is the manifestation of the electronic signature

Document Name: d5136c00009-sap-ed-3		
Document Title:	Statistical Analysis Plan Edition 3	
Document ID:	CCI [REDACTED]	
Version Label:	2.0 CURRENT LATEST APPROVED	
Server Date (dd-MMM-yyyy HH:mm 'UTC'Z)	Signed by	Meaning of Signature
30-Jun-2020 18:06 UTC	PPD [REDACTED]	Content Approval
30-Jun-2020 11:20 UTC	PPD [REDACTED]	Author Approval

Notes: CCI [REDACTED]

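### The tipping-point search has no upper limit and stops only when the result fails, so its robustness verdict depends on a limit the SAP does not state; it also omits placebo multipliers below 1, and Table 7 does not match the text

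*SAP*

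**What the plan says.** The tipping-point analysis is in SAP Appendix E and runs only if the primary result is favourable. Missing counts are imputed at the rate of the patient's own arm times δ, with separate multipliers δ_P and δ_T, both taken over an increasing range. The stated rationale is that "the ticagrelor group is assumed to worsen after withdrawal". The search rule is that "deltas will be increased starting from 1 in increments of 0.025, until a favourable primary efficacy result is no longer favourable". The next sentence gives the verdict: if significance is kept over the matrix of possible δ "combinations, the comparison is deemed robust to missing data".

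Table 7 of the same appendix restates the method with a single symbol, "For all treatment groups j=T and P with" δ multiplying the imputed values, in the same step of 0.025. Neither place gives a maximum, grid limits or a plausibility threshold. Protocol section 8.5.1 contains no tipping-point analysis, so it supplies none. SAP section 6 lists the analysis as an addition to the protocol.

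**The concern.** There are three problems.

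- **Stopping rule against verdict.** The search ends when significance is lost, while the verdict needs significance to be kept. Both can hold only over a bounded grid, and none is defined. The bound then decides the answer, and unless it is fixed beforehand it would be chosen by people who know that the primary result was favourable.
- **Direction for placebo.** Both multipliers start at 1 and only rise. A larger δ_P gives withdrawn placebo patients more events, which helps ticagrelor. The direction that weakens the comparison, δ_P below 1, is not run.
- **Text against Table 7.** Two multipliers on arm rates and one multiplier on imputed values are different analyses. A common δ leaves the ratio of the two imputed rates where it was. Scaling an imputed count also differs from scaling the rate: a zero stays zero at any δ, and non-integer counts arise.

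At stake is whether a robustness statement in the study report would mean anything definite.

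**Working it through.** **Inputs from the documents.** SAP section 1.3 assumes that "the number of VOCs has a negative binomial distribution with shape parameter 0.8". The same section plans annual rates of 2.0 on placebo and 1.0 on ticagrelor (a halving), equal allocation, follow-up of at least 1 year and 1.5 years on average, and about 90% power with 154 patients, raised to 182 for dropouts. SAP section 4.1.1 sets a two-sided 5% level for the primary endpoint.

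**Reproducing the planned power.** For the log rate ratio with 77 per arm, mean follow-up 1.5 years and dispersion k,

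var = [(1/(2.0 × 1.5) + k) + (1/(1.0 × 1.5) + k)] / 77.

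- Shape read as size 0.8, so k = 1/0.8 = 1.25: var = 3.5/77 = 0.0455, SE = 0.213, power = Φ(0.693/0.213 − 1.96) = 90.2%. This matches the SAP. Simulation with follow-up uniform on 1 to 2 years (1,500 repetitions) gives 90.9%.
- Shape read as k = 0.8: 96.5%, which does not match.

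Size 0.8 is therefore used below. The dropout rate is not stated; the sample sizes imply 1 − 154/182 = 15.4%.

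**Simulating the tipping point.** The simulation used 91 patients per arm, rates of 2.0 and 1.0 per year, and planned follow-up uniform on 1 to 2 years. Assumed: 14 withdrawals per arm (14/91 = 15.4%), at a time uniform over planned follow-up. Post-withdrawal counts were drawn from the negative binomial conditional on the observed count, with δ applied to the arm rate. Each setting used 40 imputations combined by Rubin's rules (the SAP plans 1000). The hydroxyurea covariate was left out. The first 100 trials with a favourable significant primary result were kept. A trial has tipped when p ≥ 0.05 or the estimate no longer favours ticagrelor.

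Raising δ_T alone, δ_P = 1:

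| δ_T | 1 | 2 | 3 | 5 | 10 | 20 | 50 |
|---|---|---|---|---|---|---|---|
| Tipped | 0% | 6% | 14% | 45% | 92% | 99% | 100% |
| Median rate ratio | 0.475 | 0.518 | 0.553 | 0.632 | 0.823 | 1.177 | 2.372 |

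Raising both together, as the single δ in Table 7 suggests:

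| δ | 1 | 2 | 5 | 10 | 50 | 200 |
|---|---|---|---|---|---|---|
| Tipped | 0% | 1% | 12% | 33% | 75% | 89% |
| Median rate ratio | 0.475 | 0.485 | 0.486 | 0.510 | 0.523 | 0.570 |

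With δ_T alone the search always ends in failure. With a common δ, 11% of trials had not tipped at δ = 200.

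Changing δ_P:

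- Upward with δ_T = 1: the median rate ratio falls from 0.475 to 0.445 at δ_P = 2 and 0.374 at δ_P = 5, with 0% tipped.
- Upward with δ_T = 2: the share tipped falls from 6% at δ_P = 1 to 1% at δ_P = 2 and 0% at δ_P = 3.
- Downward with δ_T = 1: 1%, 2%, 3% and 5% tip at δ_P = 0.75, 0.5, 0.25 and 0.
- Downward with δ_T = 2: 6%, 11% and 15% tip at δ_P = 1, 0.5 and 0.

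With 100 trials the Monte Carlo standard error is √(0.06 × 0.94/100) = 2.4 points at 6% and √(0.45 × 0.55/100) = 5.0 points at 45%. δ was scaled on the rate throughout, so these runs do not measure the effect of scaling imputed counts instead.

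**The case against.** The best defence is that an open-ended search is how a tipping-point analysis works: it returns a value, and readers judge whether that value is plausible. The closing text of Appendix E fits this. It does not expect every sensitivity analysis to be significant, rests assurance on similar estimates, and leaves plausibility to the study report. That stands for the tipping value. It does not rescue the sentence declaring robustness, which needs a grid the SAP never bounds. The word possible might be taken to imply a plausible range, but none is written.

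On direction, the two-way text already contains the informative row, δ_P = 1 with δ_T rising. Appendix E also says placebo patients are not expected to move to a substantially more effective treatment after withdrawal. That sentence was written for the dropout-reason imputations (pDRMI and DRMI); it is a partial reason for not lowering δ_P and no reason for raising it. The small effect of δ_P below 1 is conceded.

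Table 7 is a summary whose formulas are hard to read in the available text, and it does not say outright that δ_P equals δ_T. The fuller text, with two named multipliers and a matrix, is the likelier intention. The two places should still agree.

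A reader might infer that this is the main stress test of a positive result. Appendix E does not support that: it calls pDRMI/DRMI the most conservative approach. A reader might also infer that the Table 7 version can hardly fail. It fails much less often, but 12% of trials tip at 5 and 33% at 10.

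**Conclusion.** The point holds as a defect in a supportive analysis. The stopping rule and the robustness verdict are incompatible without a limit that the SAP does not give, and that follows from the wording alone (provided some ticagrelor patients withdraw). The simulation shows how far the limit decides the answer: a bound of 2 would leave 94% of favourable trials robust on the δ_T row, a bound of 5 would leave 55%, and a bound of 10 would leave 8%. The omitted placebo direction is secondary (6% against 11% tipped at δ_T = 2 when δ_P goes from 1 to 0.5). The mismatch with Table 7 matters more if programmed literally (45% against 12% tipped at δ = 5).

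The percentages rest on the planned ratio of 0.5, 15.4% withdrawal spread evenly over planned follow-up, and 100 trials. SAP section 3.1.4.1 records early termination, so actual follow-up and missingness will differ.

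It would be wrong to infer that the primary conclusion or its error rate is compromised. The analysis runs only after the primary test and does not feed into it.

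**What to change.** Before unblinding, amend the tipping-point text in Appendix E to:

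1. State a finite grid with a maximum δ_T and its rationale. Appendix E offers an anchor: it assumes that ticagrelor patients who withdraw for treatment-related reasons would at worst be in the position of the placebo group. Under the planned ratio that is δ_T = 1/0.5 = 2, to which a stated margin can be added.
2. Sweep δ_T at δ_P = 1 and at one or more values of δ_P below 1.
3. Not count settings with δ_P above 1 as evidence of robustness.
4. Report the tipping value, and call the result robust only if no tipping occurs within the grid.
5. Make Table 7 show the same two multipliers, applied to the arm rate as in the text.

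The cost is a small SAP edit and a few extra runs.
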